3.6 Risks and benefits

Risks

Active comparator arm:

Azithromycin is frequently prescribed for RTIs in children, particularly in the ambulatory setting (section 3.1). As outlined in section 3.3, AEs caused by drug toxicity are extremely rare when azithromycin is administered in regular doses recommended by Swissmedic and for a maximum of 5 days. They are mainly related to gastrointestinal symptoms [39]. According to the FDA-approved prescribing information [3], the most frequent AEs attributed to 5-day azithromycin treatment were diarrhea/loose stools (5.8%), nausea (1.9%), vomiting (1.9%), abdominal pain (1.9%), and rash (1.6%) (section 5.2., Table 2). A recent RCT evaluating early administration of a 5-day azithromycin treatment on recurrent severe LRTI progression in preschool children reported only mild gastrointestinal symptoms in 3 out of 223 (1.3%) children who received azithromycin [54]. These AEs were mild and did not lead to a study discontinuation. In adults, azithromycin is known to potentially elicit arrhythmias particularly in patients with preexisting cardiovascular risk factors [40]. However, the incidence of arrhythmias as a potential consequence of QT-interval prolongation in response to macrolides in absence of additional risk factors is very low in adults (<1:100,000) [41]. Also, azithromycin administration in children is not associated with QT prolongation [39, 55]. Nevertheless, as a preventive measure and to minimize the risk for AEs, an underlying cardiovascular condition has been defined as an exclusion criterion for MYTHIC (section 7.1).

Control placebo arm:

Based on the assumption of a mild, self-limiting, and immune-mediated disease course of *Mp* CAP, the risk of progression of disease without azithromycin treatment may be minimal (section 3.5). Nevertheless, strict criteria for discontinuing or modifying treatment will guarantee the safety of patients in MYTHIC and are detailed in section 6.3: “**Unblinding Procedures (Code Break)**”. Patients are closely monitored by measuring VS at home, at in-hospital visits, and in the ambulatory setting. Detailed patient information during FUP is provided by the patient self-documentation with secuTrial® or study diary (section 9.2). The possibility of contacting the TMT and/or study physician is guaranteed 24 hours a day, 7 days a week. These measures will guarantee safety in MYTHIC.

Benefit

Active comparator arm:

Azithromycin is frequently prescribed for RTIs in children and recommended for CAP by international guidelines [8, 9, 42]. However, macrolide treatment did not yet demonstrate benefit in CAP patients with *Mp* infection [13] (section 3.1).

Control placebo arm:

Withholding azithromycin treatment will reduce antibiotic exposure and the development of AMR (MYTHIC patient) and produce efficacy data that allow targeted prescription of macrolides to reduce the emergence of AMR (future patients).

Additionally, patients in both arms will benefit from close 28-day FUP in terms of monitoring and caring during the course of illness, AEs, and/or progression of disease.

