3.3 Clinical evidence to date

The antibiotics with the best minimum inhibitory concentration values against *Mp* include macrolides, tetracyclines, and fluoroquinolones [26]. Macrolide antibiotics (i.e., azithromycin, clarithromycin, and erythromycin) have a more favorable side effect profile and are therefore the first-line antibiotics for *Mp* infections in children [8, 9]. Azithromycin is the most frequently used macrolide antibiotic worldwide because of its improved tolerability (over erythromycin) and a much longer half-life that enables a 5-day treatment (compared to a 7-10-day treatment with clarithromycin) [19]. Azithromycin can be administered orally, is available in a child-friendly formulation, and has also a much better taste compared to the strong bitter intensity of clarithromycin [37], which is essential for an IMP in terms of compliance.

Azithromycin is safe and well tolerated [38]. Side effects/adverse events (AEs) associated with azithromycin are mainly related to gastrointestinal symptoms such as diarrhea, vomiting, abdominal pain, and nausea [39]. In adults, azithromycin can elicit arrhythmias as a potential consequence of QT-interval prolongation, particularly in patients with preexisting cardiovascular risk factors [40]. Given the low concentrations resulting from oral dosing of macrolides, the incidence of arrhythmias in adults in response to macrolides in absence of additional risk factors is very low (<1:100,000) [41]. The risk of cardiac toxicity in children is unknown [39]. Nevertheless, underlying cardiovascular disease is preventively listed as exclusion criteria in MYTHIC (section 7.1).

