4.5 Safety objectives

Objectives regarding safety of the placebo treatment are part of the co-primary objectives (1.2, CAP-related change in patient care status), secondary objectives (2.1, overall clinical outcome based on benefits and harms and 2.4, development of *Mp*-associated extrapulmonary manifestations), and additional objectives (unscheduled medical visits, [re-]treatment with antibiotics, side effects/AEs/SAEs of IMP). The MYTHIC Study will collect data on specific expected side effects/ AE of azithromycin in children, in particular parent reported gastrointestinal side effects (section 3.6 and section 5.2., Table 2) and discontinuation or modification of the IMP (section 6.3, Table 6, and section 7.4).

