5.2 Secondary outcomes

A number of secondary and additional outcomes have been defined as relevant endpoints for antibiotic trials in childhood CAP by the IDSA [62].

2.1: Overall clinical outcome based on benefits and harms (DOOR/RADAR approach)

According to documentation of clinical response (normalization of all VS) and solicited AEs 1x/24h at the end of treatment (day 5) and each FUP visit.

Specific measurement: Documentation of clinical response (normalization of all VS, section 5.1) and solicited AEs (Table 2) 1x/24h at the end of treatment (day 5) and at each FUP visit.

Analysis metric: Desirability of outcome ranking (DOOR) [65].

Method of aggregation: Probability of better DOOR.

Time point: Day 3 (in-hospital visit), day 5 (end of treatment), day 7, 14, 21 (phone calls), and day 28 (close-out visit).

Rationale: The novel *response adjusted for duration of antibiotic risk* (RADAR) methodology utilizes a superiority design [65]. In RADAR, all trial participants are assigned a DOOR. The DOOR is constructed using a 2-step process: (1) categorization of all patients into an overall clinical outcome (Table 3), and (2) ranking participants in the trial using 2 rules: (2a) when ranking the outcomes of 2 patients with different overall clinical outcomes, the patient with a better overall clinical outcome receives a higher rank; and (2b) when ranking the outcomes of 2 patients with the same overall clinical outcome, the patient treated with placebo receives a higher rank. These DOOR ranks are then compared between the treatment arms with regard to the probability of a better DOOR for a randomly selected patient with placebo vs. azithromycin (i.e., Wilcoxon-Mann-Whitney statistic [66]). The DOOR/RADAR approach is helpful for RCTs to define the optimal therapeutic strategy, since considering exclusively the primary endpoint may not allow researchers to accurately balance a proven benefit with other potential harms (i.e., impaired effectiveness or side effects/AEs).

Table 2: Solicited adverse events (AEs) grading [66, 67].

Symptom	Mild (grade 1)	Moderate (grade 2)	Severe (grade 3)
Diarrhea	Looser than normal stools occurring 3-6 times/day	Looser than normal stools occurring >6 times/day	Bloody diarrhea, or diarrhea that requires medical intervention, laboratory testing, or hospitalization
Vomiting	1 episode/day	2-3 episodes/day	≥ 4 episodes/day

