9.2.4.1 Adverse events (AEs)

Solicited AEs will be asked from parental report and/or will be identified in routine electronic healthcare records at participating centers. Solicited AEs are summarized in section 5.2, Table 2. These solicited AEs will be used to determine **DOOR** (section 5.2).

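### Nausea is named as a frequent azithromycin adverse event and referred to Table 2, but Table 2 has no nausea row, so it is neither systematically solicited and graded nor counted in DOOR

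*Protocol*

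**What the plan says.** Section 3.6 of the protocol introduces its list with "the most frequent AEs attributed to 5-day azithromycin treatment were diarrhea/loose stools (5.8" percent), continues with "nausea (1.9%), vomiting (1.9%), abdominal pain (1.9%), and rash (1.6%) (section 5.2., Table 2"), and so sends the reader to Table 2 for the whole list. Section 3.3 also names nausea, among "gastrointestinal symptoms such as diarrhea, vomiting, abdominal pain, and nausea", without reference to Table 2. Section 4.5 commits the trial to collecting the expected side effects of azithromycin, "in particular parent reported gastrointestinal side effects (section 3.6 and section 5.2., Table 2").

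The table referred to is "Table 2: Solicited adverse events (AEs) grading" in section 5.2. Its five rows are diarrhea, vomiting, abdominal pain, allergic reaction, and candidiasis. Section 9.2.4.1 makes it the definition of a solicited event and the input to the ranked outcome: "Solicited AEs are summarized in section 5.2, Table 2. These solicited AEs will be used to determine" DOOR. Table 3 then ranks children whose vital signs have normalized (categories 1 to 4) by the grade of their solicited adverse events alone.

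**The concern.** The protocol names a harm, points to the instrument that is to collect it, and the instrument does not contain it. Nausea is quoted at the same rate as vomiting and abdominal pain, both of which are solicited. Candidiasis is solicited although section 3.6 does not mention it. No reason is given for leaving nausea out.

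What is at stake is the completeness of the solicited adverse event table and of DOOR. DOOR is a secondary outcome, is also designated a safety outcome (section 5.4), and is meant to weigh benefit against harm. An analysis plan cannot repair this later, because events that were never asked about cannot be recovered at the analysis stage.

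**Working it through.** The plan states no figure on this point, so there is none to reproduce. The check is a comparison of the text, followed by a bound on the size.

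**Section 3.6 against Table 2**

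| Event in section 3.6 | Quoted rate | Row in Table 2 |
|---|---|---|
| Diarrhea/loose stools | 5.8% | yes; grade 1 is "Looser than normal stools occurring 3-6 times/day" |
| Nausea | 1.9% | none |
| Vomiting | 1.9% | yes, graded by episodes; grade 2 is "2-3 episodes/day" |
| Abdominal pain | 1.9% | yes |
| Rash | 1.6% | yes, under allergic reaction |

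Four of the five events have a row. The vomiting row counts episodes, starting at one per day, so nausea without vomiting cannot be graded there.

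**Other places where nausea can be recorded**

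- As an unsolicited adverse event: outcome 3.4, section 10.1 and the broad definition in Table 8. This is not asked item by item, and the only severity scale in the protocol is Table 2, which has no entry for nausea.
- As part of the combined nausea-or-vomiting item of outcome 2.2 (sections 4.3 and 5.2). There it counts as a symptom of pneumonia. The assessment list for the same outcome in section 9.2.2 names neither nausea nor vomiting.
- Neither route feeds DOOR.

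**Expected number of children**

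Section 11.2 plans 376 patients allocated 1:1, which is 376 / 2 = 188 per arm. At the quoted rate, 188 × 0.019 = 3.6 azithromycin children. This is an upper bound at that rate, because a nauseated child who also vomits or has another solicited event already leaves category 1.

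**Effect on DOOR**

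Assumptions: all children normalize vital signs; nausea is grade 1 and occurs without another solicited event; the quoted rate applies at the assessment considered; other solicited events are all placed in one category. Let a and p be the proportions with any solicited event under azithromycin and placebo.

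- Without the tie-break (ties count one half), the probability of a better outcome with placebo is 0.5 + 0.5 × (a − p). Adding 1.9% nausea under azithromycin only shifts it by 0.5 × 0.019 = 0.0095, for example from 0.500 to 0.5095. Equal nausea in both arms shifts it by 0.
- With the rule that placebo wins ties, the probability is 1 − p × (1 − a).

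| a, p before | Nausea added (azithromycin, placebo) | Before | After | Shift |
|---|---|---|---|---|
| 0.30, 0.30 | 0.019, 0 | 1 − 0.30 × 0.70 = 0.790 | 1 − 0.30 × 0.681 = 0.7957 | +0.006 |
| 0.112, 0.112 | 0.019, 0 | 1 − 0.112 × 0.888 = 0.9005 | 1 − 0.112 × 0.869 = 0.9027 | +0.002 |
| 0.112, 0.112 | 0.019, 0.019 | 0.9005 | 1 − 0.131 × 0.869 = 0.8862 | −0.014 |
| 0.112, 0 | 0.019, 0.019 | 1.000 | 1 − 0.019 × 0.869 = 0.9835 | −0.017 |

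The value 0.112 is the sum of the other four quoted rates (5.8 + 1.9 + 1.9 + 1.6 = 11.2%). The values 0 and 0.30 are assumed extremes. The sign changes because a missing category creates ties, and the rule awards every tie to placebo.

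**The case against.** The strongest reply is that nausea is not missing from the trial. Adverse events of the study drug are a separate outcome (3.4), not confined to Table 2. Section 9.2.4 lists them apart from DOOR. Table 8 defines an adverse event broadly enough to include nausea. Symptom reviews that include adverse events are held at every visit and phone call and, until vital signs normalize, daily. Section 11.4.5 promises frequencies and types of adverse events by arm. All of this stands. A reader might infer that a known harm of azithromycin will go unreported, or that section 10.1 limits adverse event collection to Table 2. The documents do not support either: section 10.1 cites section 9.2.4 as well as Table 2.

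A second reply is that the set of solicited items is a design choice, that Table 2 cites two earlier trials for its grading, and that nausea in a young child is a subjective parental report. That would be a fair reason to leave nausea out, but the protocol does not give it, and sections 3.6 and 4.5 point the other way. It can also be said that section 4.5 does not promise a row for every event in section 3.6. That is literally true, yet section 3.6 attaches Table 2 to a list that contains nausea.

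A third reply is that the effect is trivial. It is small, as the bounds show, and it reaches no co-primary outcome, margin, sample size or error rate.

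**Conclusion.** The mismatch is real and minor. Nausea is named, is referred to Table 2, and is absent from it. It is therefore not systematically solicited or graded as an adverse event, and nausea alone leaves a child with normalized vital signs in DOOR category 1.

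The size is at most about 3.6 of 188 azithromycin children. The DOOR probability moves by 0 to about 0.01 without the tie-break and by about −0.017 to +0.006 with it. These bounds rest on the quoted 1.9%, on placebo nausea between 0 and 1.9%, and on the simplifying assumptions stated with the calculation.

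It may be tempting to conclude that azithromycin will look better tolerated than it is. That follows only for the comparison without the tie-break, and only if nausea is more frequent with azithromycin. Under the placebo-wins-ties ranking the direction is not fixed.

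**What to change.** Reconcile sections 3.6 and 4.5 with Table 2. The preferred way is to add a graded nausea row to Table 2, so that nausea enters the solicited adverse event table and DOOR. This costs one table row and one field in the eCRF and diary, if the parameter list (Appendix 2, not shown) does not already have it. The downside is more mild, subjective events in both arms.

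If the sponsor prefers not to solicit nausea, the protocol should say so and correct the cross-references in sections 3.6 and 4.5, which costs only a text change.

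In either case, align the outcome 2.2 symptom lists in sections 5.2 and 9.2.2 with each other. The combined nausea-or-vomiting item need not be split, so the validated symptom measure can stay as it is.

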3.7 Justification of choice of study population

CAP is the leading cause of hospitalization in children and adolescents in high-income settings [7-9]. However, the etiology and pathophysiology of CAP differs considerably between adults and children [7, 56, 57]. Therefore, observations from adult CAP studies do not necessarily apply to a pediatric population [6]. In 2017, 1361 children aged 1-14 years have been hospitalized with pneumonia in Switzerland according to the Federal Office of Public Health (FOPH). This represents an incidence of 115 cases per 100,000 individuals in this age group. *Sp* and *Mp* are the two major bacterial causes of pneumonia in hospitalized children [14]. Over the past three decades, *Sp* conjugate vaccines have markedly reduced the incidence of pneumococcal pneumonia so that *Mp* emerged to be the most frequently detected pathogen causing bacterial CAP in hospitalized U.S. children. *Mp* is detected most

frequently in school-aged children with CAP [17-20], with a prevalence of 18% (5-9 years [21]), 19% (5-17 years [7]), and 29% (3-17 years [22]), respectively. The estimation of the *Mp* CAP disease burden would even be higher considering cases not only managed in hospitals but also by primary care physicians. Overall, these numbers demonstrate the on-going burden of childhood CAP, and particularly *Mp* CAP, in the Swiss healthcare landscape. Thus, MYTHIC will recruit children aged 3-17 years with *Mp* CAP (section 7). No competing trials recruiting children with CAP is being conducted in Switzerland from the start of MYTHIC.

Tailored prescription of antibiotic treatment is needed to minimize selection of antibiotic resistant pathogens [39]. Thus, reducing the excessive use of macrolides is an important target [13, 25, 58]. In Switzerland, azithromycin, a macrolide antibiotic, is frequently used for RTIs based on its good taste, excellent tolerability, its short regimen duration, and its once daily dosing (www.swisspeddose.ch). In the U.S., macrolides are the most common antibiotics prescribed during ED visits for childhood pneumonia, and accounted for nearly half of all antibiotics given to children [59]. However, the widespread use of macrolides has led to a global emergence and spread of MRMP [27]. The most recent MRMP prevalence of 9% (2014-2017) shows that macrolide resistance is a relevant issue in Switzerland [29], even more considering past macrolide-resistant *Sp* prevalence of 10-20% (2004-2014) [60]. The targeted prescription of macrolides is therefore a priority in Switzerland. Previous studies failed to successfully demonstrate a treatment effect of macrolides for *Mp* CAP. Therefore, the proposed MYTHIC Study is a unique opportunity to produce the first worldwide available efficacy data for the use of macrolides in childhood *Mp* CAP. By using the novel IgM ASC ELISpot assay, which is so far the only test accurately differentiating between *Mp* carriage and infection, this study will generate reliable efficacy data impacting macrolide administration for childhood *Mp* CAP in Switzerland and worldwide. With these prospects this study will be of particular significance for pediatric antibiotic administration in Switzerland. On a global scale, this study will provide vital information for reducing macrolide resistance in *Mp* and other bacteria causing pediatric CAP. The results of this study will be immediately relevant to the authorities providing guidance on the treatment of childhood CAP in Switzerland and worldwide. Overall, the study results will have a direct impact on the management and antibiotic prescription strategies for childhood respiratory diseases. Finally, these results will potentially lead to a global reduction of the over-prescription of macrolides in pediatric infectious diseases leading to reducing the spread of MRMP.

4. STUDY OBJECTIVES

4.1 Overall objective

The overall objective of MYTHIC is to produce efficacy data allowing targeted prescription of macrolides in pediatric *Mp* CAP (immediate effect) for reducing the emergence of AMR (longer term effect). This will consist of:

- Evaluating the efficacy of macrolide antibiotics vs. placebo on VS abnormalities and symptom duration; and
- Evaluating the safety of macrolide antibiotics vs. placebo in terms of change in patient care status, such as (re-)admission or an ICU transfer.

Furthermore, MYTHIC will investigate the influence of macrolides on bacterial clearance and AMR development (antimicrobial effects), as well as inflammation and host immunity (anti-inflammatory effects) in *Mp* CAP.

4.2 Co-primary objectives

This study aims to show in ambulatory and hospitalized children aged 3-17 years with *Mp* CAP that treatment with placebo is non-inferior to treatment with azithromycin in terms of (1.1) efficacy and (1.2) safety:

1.1: Efficacy: Time to normalization of all VS, including body temperature (T), respiratory rate (RR), heart rate (HR), and saturation of peripheral oxygen (SpO₂).

Hypothesis: The administration of a placebo in pediatric *Mp* CAP will be non-inferior with respect to the duration of VS abnormalities compared to a 5-day azithromycin regimen.

1.2: Safety: CAP-related change in patient care status, such as (re-)admission or ICU transfer, within 28 days after the index episode.

Hypothesis: The administration of a placebo in pediatric *Mp* CAP will be non-inferior with respect to the CAP-related change in patient care status compared to a 5-day azithromycin regimen.

4.3 Secondary objectives

The secondary objectives include the evaluation of:

2.1: Overall clinical outcome based on benefits and harms (desirability of outcome ranking [DOOR] and response adjusted for duration of antibiotic risk [RADAR] approach).

2.2: Time (days) to normalization of CAP-related symptoms (i.e., cough, shortness of breath, wheeze, chest pain, sore throat, nasal congestion or runny nose, headache, muscle aches or pains, nausea or vomiting, diarrhea, reduced general condition, decreased appetite, not sleeping well, reduced activity).

2.3: Quality of life (QoL) assessment of the patient's family.

2.4: Time (days) to return to the patient's daily routine, defined as return to childcare/school/work of patients and their families.

2.5: Development of *Mp*-associated extrapulmonary manifestations.

4.4 Additional objectives

Additional objectives include the evaluation of:

3.1: Length of hospital stay (LOS).

3.2: Unscheduled medical visits.

3.3: (Re-)treatment with antibiotics and total antibiotic exposure.

3.4: Side effects/ AEs/ serious AEs (SAEs) of IMP.

3.5: Antimicrobial/anti-inflammatory effects.

Other additional objectives independent of study intervention include the evaluation of:

4.1: Parent's perception of informational video about the study.

Exploratory subgroup analyses will assess the interaction between subgroup variables and treatment. The subgroup variables will include age, sex, patient care status, prodromal symptom duration, IgM ASC ELISpot-confirmed *Mp* infection, and radiological evidence of CAP.

4.5 Safety objectives

Objectives regarding safety of the placebo treatment are part of the co-primary objectives (1.2, CAP-related change in patient care status), secondary objectives (2.1, overall clinical outcome based on benefits and harms and 2.4, development of *Mp*-associated extrapulmonary manifestations), and additional objectives (unscheduled medical visits, [re-]treatment with antibiotics, side effects/AEs/SAEs of IMP). The MYTHIC Study will collect data on specific expected side effects/ AE of azithromycin in children, in particular parent reported gastrointestinal side effects (section 3.6 and section 5.2., Table 2) and discontinuation or modification of the IMP (section 6.3, Table 6, and section 7.4).

